If the null hypothesis for Hypothesis 2A is rejected, Hypothesis 2B will be tested at Week 12 for the total number of bleeding sites.

Hypothesis 2B:

Null: The mean is equal between the Experimental Toothpaste #1 Group and Negative Control Group.

Alternative: The mean is not equal between the Experimental Toothpaste #1 Group and Negative Control Group.

If the null hypothesis for Hypothesis 2B is rejected, subsequent analyses will compare the experimental groups with the positive control group at Week 12. These analyses will focus on the total number of bleeding sites, consistent with the study's primary objective. Percent number of bleeding sites, LSGI score, Week 4 and Week 12 visits, and all other treatment comparisons will also be analyzed. No adjustment will be made for multiple comparisons.

Safety Analysis

Summary tables will be provided for all reported AEs by MedDRA code and treatment group with safety analysis set. Tables will also be provided for all reported AEs by MedDRA code and subject.

Number of Subjects Planned to Be Enrolled

Power analyses were conducted with $\alpha=0.05$, using a 2-sided test. Up to 120 subjects will be enrolled in the study assuming ~5% dropout rate. Data were utilized from a similarly designed study with the same examiner and endpoints (from 2020054).

Twenty-eight subjects per group completing this trial should provide at least 80% power to detect a difference in number of bleeding sites of at least 8 units between treatments assuming the variability (SD) number of bleeding sites is 10. Assuming the variability (SD) of whole mouth LSGI is 0.1, a sample size of 28 subjects per group should provide at least 80% power to detect a difference in LSGI of at least 0.08 units between treatments.

Level of Significance

The level 0.05 of significance will be used for treatment comparisons.

Termination Criteria

Early termination is not anticipated for this study.

Procedure for Missing, Unused and Spurious Data

Unless noted otherwise, missing data will not be imputed. All analyses will be based on observed data only.

Procedure for Reporting Deviations from the Original Statistical Plan

When differences exist in descriptions or explanations provided in this protocol and the Statistical Analysis Plan (SAP), the SAP takes precedence; the differences will be explained in the clinical study final report.

Subjects to be Included in the Analyses

The following populations are defined for the purpose of the analysis:

Intent-to-treat (ITT) Population

The ITT population will include all randomized subjects who are confirmed to have received study treatment and have at least one post-treatment efficacy measurement. This will be the primary population for the analysis of efficacy endpoints.

Per Protocol (PP): All subjects who received study treatments and completed the study per protocol (also known as “evaluable population”).

Safety Analysis Set: All subjects who received study treatments and had oral examinations conducted will be included.

Direct Access to Source Data/Documents

The Investigator has the responsibility for ensuring that all source documents (*i.e.*, study and/or medical records) and CRFs are completed and maintained according to the study protocol and local regulations and are available at the site. Any CRF used as a source document must be identified as such in the Investigator Notebook.

The Data Manager will supply the paper and/or eCRFs to be used in this study. It is the responsibility of the Investigator to maintain and submit accurate and timely CRFs to the Sponsor. All hard copy CRFs will be filled out legibly in ink.

All questions should be answered. For paper CRFs, if an entry requires correction, a single line will be placed through the entry so as not to obscure the original record, the corrected entry will be initialled and dated by the individual making the change, and a reason will be given for the change. There will be no whiteouts or erasures. For eCRFs, if an entry requires correction, the change is made directly to the CRF in the database, the user is prompted to provide a reason for the change, and the correction is logged in by an electronic audit trail.

As necessary, the Data Manager may make specified allowable changes to the database without issuing a query to the site, as agreed upon by study site staff per this protocol. Examples of allowable changes include incorrect date formats, incorrect current year recorded (as in the start of a new year), and unambiguous spelling errors. Changes to common abbreviations and symbols to equivalent text to meet system or coding constraints (*e.g.*, @ = at, ~ = approximately), may also be allowable. Values that are ambiguous or open to interpretation will be queried to the sites' staff. It is the responsibility of the Data Manager to ensure all changes are supported by information contained elsewhere and/or are unambiguous.

Quality Assurance and Quality Control

The following steps will be taken to ensure the accuracy, consistency, completeness and reliability of the data:

- Creating Clinical Trial Risk Assessment and Risk Management Plan;
- Site initiation meeting;
- Routine site and/or data monitoring;
- eCRF review against source documents;
- Data management quality control checks;
- Statistical quality control (QC) checks;
- Continuous data acquisition and cleaning; and
- Internal review of data.

In addition, a Sponsor representative may conduct periodic quality assurance audits of the study processes, including, but not limited to, clinical site visits, laboratories, vendors and contract research organizations, the study database, and Procter & Gamble's final study report. Data monitoring will ensure quality of collected information by detection of inconsistent and missing information. The investigational site staff will follow up on any queries from Procter & Gamble's Data Manager. If a query arises from a subject that was lost to follow-up, the site staff will take action to contact the subject and document any attempts made. The study monitor will ensure that the study was conducted in accordance with the protocol and any amendments, good epidemiological practice, and applicable laws and regulations. The quality assurance and quality control systems implemented to assure the quality of the data should be described.

Ethics Description and Ethical Considerations

Subject participation is voluntary. Subjects have a right to refuse participation in the research study at any stage. The study will be conducted in accordance with all international laws and regulations, and also Canadian national laws and regulations, and in accordance with any applicable guidelines. Informed consent will be obtained from potential subjects of the study. Beforehand, the study site staff should fully inform each subject regarding all the aspects of the clinical study, including objectives, collected data, expected risks and benefits of participation, and voluntary participation in the study.

Conduction of the study will comply with the principles of ICH-GCP. Before the study starts an approval of independent ethical committee for conduction of the present study will be obtained. A list of Investigators and investigational sites will be approved. All documents and data related to

the study are strictly confidential. Protocol contents cannot be disclosed to third parties without written permission of the Sponsor.

Sponsor of the study is obliged to adhere to confidentiality of the study subjects' personal data. Any information identifying the subject's identity should not be disclosed. The necessary personal data of the subjects as part of the study (for example, gender, age) will be collected only for achieving study purposes and in minimum quantity. The study site staff will maintain an identification list of all screened and enrolled subjects. This information will only be accessible to the project team members that perform pertinent study execution tasks and/or GCP monitoring. Names and surnames of subjects will not be disclosed or reported to other project team members. If subject name and surname are mentioned in any document, then before sending a copy of such document to the Sponsor these data will be erased. Results of the study stored in electronic format will be kept in accordance with current information protection laws. Sponsor employees or regulatory authorities' representatives should not contact the subject directly. Before enrollment into the study, subjects will be informed regarding confidentiality provisions and use of their personal data, including necessity of access to them of the monitor and other authorized people (in case of auditing, inspection, *etc.*).

Prior to study initiation, the Investigator must obtain institutional review and approval of the Protocol, the consent form, and other necessary study-related documents in compliance with the Part 4 of the NHPR or the ICH-GCPs Consolidated Guidelines, Chapter 3 and in compliance with Procter & Gamble's Standard Operating Procedure (SOP) CTN-CL-504 ("Institutional Review Board/Independent Ethics Committee Review and Approval"). The Investigator will maintain any original authorization letter(s) which will be available for review by the Sponsor. IRB approval letters should include the study title, Sponsor study number, the address of the IRB, date of request, and the signature of the IRB chairperson or designee. Additionally, the letter must acknowledge that both the Protocol and consent form have been approved by the IRB. The study will not begin until the Sponsor has received confirmation of IRB approval. The IRB shall also review the investigation at least once a year during study execution. The Investigator will notify the IRB when the study is terminated and provide confirmation that the study has been closed with the IRB to the Sponsor.

The Investigator will obtain written informed consent for each subject prior to participation in the study, per Section 74(h) of the NHPR and ICH-GCPs, Chapter 4, Subpart 4.8 and in compliance with Procter & Gamble's SOP CTN-CL-503 ("Informed Consent Form, Ethics Approval and Investigator Use"). Subjects, or their legal guardian, are required to read, sign, and date an IRB approved consent form with the Investigator also maintaining a signed and dated copy. The subject or legal guardian will be given a copy of the consent form. All study procedures must be explained in non-technical terms.

Changes to the Protocol following IRB approval affecting the safety of subjects, scope or objectives of the investigation, or the scientific quality of the study will be documented as amendments. Such changes will require the Sponsor, Investigator, IRB, and NNHPD approval prior to implementation, unless immediate action is required to safeguard subject safety. Administrative or minor changes (*e.g.*, typographical errors, changes in Sponsor personnel, *etc.*) will be documented as revisions but may not need to be submitted as amendments unless required

by the IRB. Any change in the Sponsor's monitoring staff, Clinical Trial Manager or Medical Monitor during the conduct of the study, will be reported to the Investigator.

During the course of the trial, the clinical site will allow monitoring by the Sponsor (Clinical Trial Manager or designee) to check compliance with the Protocol, regulations and guidelines, adequacy of the equipment and facilities, and satisfactory data collection.

Data Handling and Recordkeeping

The Investigator must retain the subject identification codes, informed consent documentation, clinical materials inventory, CRFs (paper or electronic media), medical records and other source data for a minimum of 15 years after the last regulatory approval has been received or the discontinuation of the study. The Investigator must receive written authorization from the Sponsor before destroying any study document. The Investigator will make the records available for inspection and copying upon the request of an authorized employee of a government authority or the Sponsor, at reasonable times. In the event the Investigator retires, relocates, or for any other reason withdraws from the responsibility for maintaining records for the period of time required, custody of the records may be transferred to another person who will accept responsibility for the records. Notice of such a transfer must be given in writing to the Sponsor.

The subject will be identified with a unique identification code assigned by the Investigator to each trial subject to protect privacy. The identification codes are used in lieu of the subject's name when the Investigator reports all AEs and other trial -related data. These codes will be used on all study documents for the subject's confidentiality, as stated in Section 2.11 of the ICH-GCP.

Any advertisements used in recruitment of subjects must receive prior approval from Procter & Gamble and/or the Investigator's IRB. A copy of the IRB-approved advertising and the documentation thereof must be provided to Procter & Gamble.

Following completion of the study, the Investigator shall submit a final report to the Sponsor describing the conduct of the study, deviations from planned conduct, early withdrawals and Subject Accountability, AEs, and other information on study conduct. The Investigator's IRB may require more frequent status reports.

Financial Statement

Financing and insurance can be found in signed and executed clinical study agreement.

Publication Policy

The results of this study may be published in oral presentations, written abstracts, written manuscripts, and/or with regulatory agency.

Supplements

This section is not applicable to this protocol.

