Subjects will be stratified based on the baseline number of bleeding sites, age, and gender (bleeding and age cut-offs based on data from 2020054 study). Subjects will be randomly assigned in approximately equal numbers to 1 of the 4 treatment groups using an encoded program supplied by the Sponsor. Subjects residing in the same household will be assigned to the same treatment group. The examiner will be in an area separate from randomization and product distribution.

Table 2. Basic Study Design Information

STUDY DESIGN	N	N/GROUP	B&A PROGRAM	BLOCK SIZE	STRATA	CUT-OFFS	SAME HOUSEHOLD
Parallel	120	30	Yes	4	Bleeding Sites	≤30%, >30% and ≤58%, or >58%	Yes
					Age	≤ 50 or >50	
					Gender	Male or Female	

B&A = Balance and Assignment.

Balance and Assignment (B&A) Program

At the baseline visit, subjects will be randomly assigned to 1 of the 4 treatment groups (up to 30 per group) using an encoded B&A program supplied by the Sponsor. The subjects will be stratified based on total number of bleeding sites, gender, and age. Subjects residing in the same household will be assigned to the same treatment group.

Blinding

Identities of the study investigational products will be disguised with a permanent study label. Products that are purchased from the marketplace (e.g., negative and positive controls) will be over-labeled with a permanent generic white label that is similar to the experimental toothpastes to maintain the study blind. Additionally, toothpastes will be over-labeled by personnel not associated with the study assigned and will be distributed to participants in a concealed to ensure study blinding. When possible, similar sized kit boxes/tubes/bottles will be used to ensure product blinding. All treatment products will be dispensed in a secluded area, away from the study examiner(s), to maintain the study blind.

Subject treatment(s) will only be distributed to select site personnel responsible for usage instruction and supervised use.

White opaque cardboard take-home kit boxes will contain 3 tubes of toothpaste in plain white tubes, a manual toothbrush, timer, and instruction sheet. All treatment products will be used at home twice daily as instructed on the instruction sheet for 12 weeks.

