General Comments can be recorded at any time during the study. AEs will be documented in eCRF. Any subject reported AE that remains unresolved by the end of the study should be followed up until resolution by the Investigator/designee. Examiner-observed AEs that are unresolved at the end of the study are followed up to resolution at the discretion of the Medical Monitor. All resolutions should be documented only as source documentation. If a subject is unreachable to determine whether the AE has been resolved, the attempts to contact the subject should be documented as source documentation.

Statistics

Statistical Methods

Summary statistics (*e.g.*, means, standard deviations, frequencies.) of the demographic characteristics will be calculated for each treatment group and overall. Gingivitis scores will be calculated for each treatment group and visit.

Primary Efficacy Analysis

Comparisons to baseline will be investigated using paired-difference t-tests. The treatment groups will be compared using the analysis of covariance method with baseline as a covariate. If normality assumptions are not satisfied, transformation of the data and/or non-parametric analyses may be carried out. Statistical tests for treatment comparisons will be two-sided using a 5% significance level. No adjustment will be made for multiple comparisons. Additional analyses may be performed to fully understand the data.

The following hypotheses will be tested using a serial gatekeeping approach. Using this approach, differences between groups are tested in accordance with a pre-defined hierarchical approach such that the subsequent comparison is statistically tested only if the null hypothesis for the prior test is rejected. The hierarchical approach is detailed below.

For model sensitivity Hypothesis 1 will be tested at Week 12 for the total number of bleeding sites.

Hypothesis 1:

Null: The mean is equal between the Positive Control Group and Negative Control Group.

Alternative: The mean is not equal between the Positive Control Group and Negative Control Group.

If the null hypothesis for Hypothesis 1 is rejected, Hypothesis 2A will be tested at Week 12 for the total number of bleeding sites.

Hypothesis 2A:

Null: The mean is equal between the Experimental Toothpaste #2 Group and Negative Control Group.

Alternative: The mean is not equal between the Experimental Toothpaste #2 and Negative Control Group.

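### Household members share one treatment group, but the ANCOVA and the sample size treat every subject as independent, so the 5% level can be exceeded if households enrol together and their outcomes correlate

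*Combined protocol and SAP*

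**What the plan says.** The Randomization section states "Subjects residing in the same household will be assigned to the same treatment group". The Balance and Assignment (B&A) Program section repeats the rule, and Table 2 carries it as a design feature (same household: yes). The documents set no limit on subjects per household and give no expected number of shared households.

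Under Primary Efficacy Analysis, "The treatment groups will be compared using the analysis of covariance method with baseline as a covariate". No household term, random effect or robust standard error is named. "Statistical tests for treatment comparisons will be two-sided using a 5% significance level". Hypotheses 1, 2A and 2B are tested in sequence with this method. The t-test has a different role: "Comparisons to baseline will be investigated using paired-difference t-tests".

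The section on the number of subjects says "Twenty-eight subjects per group completing this trial should provide at least 80% power"; the target is a difference of 8 bleeding sites, with an assumed SD of 10. On enrolment it says "Up to 120 subjects will be enrolled in the study assuming ~5% dropout rate". Household sharing does not appear there, in the missing-data section or in the analysis populations. The list of data entered directly in the eCRF names no household identifier.

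**The concern.** A second or later member of a household is not randomised independently; that person takes the arm the household already has. Within an arm, such subjects form clusters. Gingivitis is plaque-induced, as the protocol's Summary of Findings says, and people who live together may share diet and hygiene habits, so some positive correlation in their outcomes is plausible.

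An ANCOVA that treats clustered subjects as independent credits the trial with more information than it has. Its standard errors are then too small, and each nominal 5% test rejects a true null hypothesis too often. Hypothesis 1 opens the testing sequence, so the question bears on the gate, on the two hops comparisons behind it and on all later between-group comparisons. The power statement also counts more independent subjects than the trial would have.

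**Working it through.** **Inputs from the documents.** Difference 8 bleeding sites, SD 10, two-sided alpha 0.05, 28 completers per group, about 5% dropout, 120 enrolled.

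**Inputs that are assumed.** Share of subjects in shared households, f, from 0 to 50%; ICC of the baseline-adjusted outcome, 0.1 to 0.5; two members per shared household.

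**Step 1: the plan's own figure.** The normal formula gives n = 2(1.960 + 0.842)² × 10²/8² = 24.5, so 25 per group; the t-based calculation gives 26. With 28 per group the standard error of a difference is 10 × √(2/28) = 2.673 and the noncentrality is 8/2.673 = 2.993. Power is 83.6% with 54 df (two groups) or 84.3% with 107 df (four-group ANCOVA, 112 − 5). Then 28/0.95 = 29.5, so 30 per group and 120 in all. The stated figure is met if subjects are independent.

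**Step 2: formulas under household sharing.**

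- Design effect for pairs: DE = 1 + f × ICC.
- True standard error = ANCOVA standard error × √DE.
- True two-sided level of the unadjusted test = 2 × [1 − Φ(1.96/√DE)].
- Effective number per group = 28/DE.
- Power once the standard error is right: t-test with noncentrality 2.993/√DE.

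Example, f = 20% and ICC = 0.3: DE = 1 + 0.2 × 0.3 = 1.06; √1.06 = 1.030; 1.96/1.030 = 1.904; two-sided tail 5.7%; effective n = 28/1.06 = 26.4.

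| f | ICC | DE | True level | Effective n per group | Power, 54 df / 107 df |
|---|---|---|---|---|---|
| 0 | any | 1.00 | 5.0% | 28.0 | 83.6% / 84.3% |
| 10% | 0.1 | 1.01 | 5.1% | 27.7 | 83.3% / 83.9% |
| 10% | 0.3 | 1.03 | 5.3% | 27.2 | 82.6% / 83.2% |
| 20% | 0.3 | 1.06 | 5.7% | 26.4 | 81.5% / 82.2% |
| 30% | 0.3 | 1.09 | 6.1% | 25.7 | 80.4% / 81.1% |
| 40% | 0.5 | 1.20 | 7.4% | 23.3 | 76.5% / 77.3% |
| 50% | 0.5 | 1.25 | 8.0% | 22.4 | 74.8% / 75.6% |

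Power reaches exactly 80% at DE = 1.10 (54 df) or 1.12 (107 df).

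**Step 3: check by simulation.** A four-group ANCOVA with 28 per group and equal numbers of pairs in each group gave a type I error of 5.0% with no pairs, 5.7% at f = 21%, ICC 0.3, and 8.1% at f = 50%, ICC 0.5. The formula gives 5.0%, 5.7% and 8.0%. At f = 7%, ICC 0.3 one short run gave 4.7%; a repeat with 100,000 runs gave 5.3%, against 5.2% from the formula. At that end the inflation is small enough for simulation error to hide it.

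**Larger households.** For size m, DE = 1 + f(m − 1)ICC. With m = 3, f = 20% and ICC 0.3 it is 1 + 0.2 × 2 × 0.3 = 1.12, against 1.06 for pairs.

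**The case against.** The strongest reply is that nothing shows the problem will occur. The household rule says what happens if people from one household enrol, not that any will. The ICC that matters is the one left after baseline adjustment, and baseline may absorb part of any stable shared habit. At f = 10% and ICC 0.1 the level is 5.1%, which is negligible. All of this stands. A reader might infer that the 5% level is exceeded, that every between-group test is anti-conservative and that the trial is underpowered. The documents support none of these, because they give neither f nor the ICC, and the planned power has some slack.

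A reader might also fault the t-test. It is a paired comparison to baseline and does not test Hypotheses 1, 2A or 2B; the point concerns the ANCOVA.

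Age and gender are stratification factors but are not named in the model. If they are prognostic, leaving them out tends to overstate the standard error, which would offset part of a household effect. The documents give no means of showing that the two cancel.

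Finally, the protocol says that the SAP takes precedence where the two differ, and the supplied file contains no separate SAP text, so a household provision may exist there. Applying the rule also requires someone to identify households, so an identifier may already be held outside the eCRF. These points limit what can be concluded, but they do not remove the mismatch in the text as supplied.

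**Conclusion.** The point holds as a conditional one. The plan allocates by household where members enrol together, and it analyses and sizes the trial as if all subjects were independent. The ANCOVA is anti-conservative only if two conditions are met: more than one member of some households enrols, and their baseline-adjusted outcomes are positively correlated.

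Under the assumed range, with pairs, the true level runs from 5.0% with no sharing to about 7.4% at f = 40%, ICC 0.5, and 8.0% at f = 50%, ICC 0.5. With little sharing or a low ICC it is about 5.1% to 5.3%. The claim of at least 80% power survives up to a design effect of about 1.10 to 1.12, so only the upper part of the range breaks it. The size is modest and uncertain. The gap still merits correction, because the remedy is cheap and is best fixed before unblinding.

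**What to change.** Carry a household identifier into the analysis database, as one eCRF field or from the record used to apply the household rule. Pre-specify household as the cluster in every between-group test (Hypotheses 1, 2A and 2B, the comparisons with the positive control, and the secondary endpoints). Either of two methods will do: cluster-robust standard errors with a small-sample correction (CR2), or a random household intercept in the ANCOVA. For any non-parametric fallback, permute by household. In the section on the number of subjects, state the expected number of shared households and the design effect it implies.

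The cost is analysis wording and at most one data field, with no extra subjects. If many households share, intervals widen: the true standard error is √1.06 = 1.030 times the unadjusted one at f = 20%, ICC 0.3, and √1.20 = 1.095 times at f = 40%, ICC 0.5. If few share, results hardly change.

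### Age group and gender are randomisation strata but not terms in the primary ANCOVA; adding them costs almost nothing and keeps the standard error honest if they are prognostic

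*Combined protocol and SAP*

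**What the plan says.** The Randomization section of the combined protocol and SAP states: "Subjects will be stratified based on the baseline number of bleeding sites, age, and gender". Table 2 gives three bleeding levels (cut at 30% and 58%), two age levels (cut at 50) and two genders, which makes 12 strata, with a block size of 4. Subjects are "randomly assigned in approximately equal numbers to 1 of the 4 treatment groups". The same section adds a household rule: "Subjects residing in the same household will be assigned to the same treatment group".

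Under Primary Efficacy Analysis the model is: "The treatment groups will be compared using the analysis of covariance method with baseline as a covariate". No supplied text adds age, gender or stratum to it, or explains leaving them out. On the significance level: "Statistical tests for treatment comparisons will be two-sided using a 5% significance level".

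Under Number of Subjects Planned to Be Enrolled: "Twenty-eight subjects per group completing this trial should provide at least 80% power", for a difference of 8 bleeding sites with SD 10, "using a 2-sided test".

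**The concern.** Stratified allocation balances a factor across the groups. If that factor is prognostic, balance lowers the true sampling variance of the treatment difference. A model without the factor leaves its variation in the residual, so the reported standard error does not reflect the reduction. The p-values then run slightly high and the confidence intervals slightly wide.

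The point is confined to age group and gender. Baseline bleeding, the factor closest to the outcome, enters through the covariate. (The strata are cut on the percentage of sites and the endpoint is a count, but the two measure the same thing.)

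The tests run in series: positive against negative control first, then each experimental toothpaste against negative control. A small loss at each step therefore affects whether the comparisons with the positive control are reached at all.

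**Working it through.** **Inputs from the document.** 28 completers per group, difference 8, SD 10, two-sided α = 0.05, four groups, up to 120 enrolled.

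**Assumptions.** SD 10 is taken as the residual SD after baseline; the document does not say which SD it is. R² is the share of that residual variance explained by age group and gender. It is not given, so a range of 0 to 0.10 is shown.

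**1. The plan's own figure.** SE of a pairwise difference = 10 × √(2/28) = 2.673, and 8/2.673 = 2.993. Power is 84.9% by the normal approximation, 83.6% by a two-sample t test (54 df), and 84.3% with the pooled four-group residual (112 − 5 = 107 df). The stated figure of at least 80% is reproduced.

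**2. Standard error.** With ideal balance the true SE is 2.673 × √(1 − R²), while the baseline-only model goes on reporting about 2.673.

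**3. Type I error, baseline-only model** = 2 × [1 − Φ(1.96/√(1 − R²))].

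**4. Power, baseline-only model.** Balance also shrinks the true variance here, so power ≈ Φ[(2.993 − 1.982)/√(1 − R²)], where 1.982 is the critical t value on 107 df. At R² = 0.10 this is Φ(1.011/0.949) = Φ(1.066) = 85.7%. At R² = 0 the formula gives 84.4%; the table shows the noncentral t value.

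**5. Power, adjusted model.** Noncentral t with 105 df and noncentrality 2.993/√(1 − R²).

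| Assumed R² | True SE | Reported SE too large by | Type I error, baseline-only | Power, baseline-only | Power, adjusted |
|---|---|---|---|---|---|
| 0 | 2.673 | 0% | 5.0% | 84.3% | 84.3% |
| 0.03 | 2.632 | 1.5% | 4.7% | 84.8% | 85.3% |
| 0.10 | 2.535 | 5.4% | 3.9% | 85.7% | 87.8% |

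Before rounding, the like-for-like power gain is about 0.6 points at R² 0.03 and 2.2 points at 0.10.

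**6. Check by simulation** (12 strata, blocks of 4, four groups). With 120 subjects, the baseline-only model's mean SE against the actual SD of the estimate was 2.58 against 2.53 at R² 0.05, and 2.58 against 2.48 at 0.10. Type I error was 4.3% and 4.1% baseline-only, and 4.8% and 5.0% with age and gender added (simulation error about 0.35 points). With 112 completers, power was 84.2% against 85.5% at 0.05 and 85.1% against 87.4% at 0.10.

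**7. The serial tests.** Assume every active group truly differs from negative control by 8. The simulated chance of rejecting all three null hypotheses, baseline-only against adjusted, is 68.2% against 68.2% at R² 0, 68.8% against 70.0% at 0.03, and about 70.2% against 74.2% at 0.10.

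**8. The household rule.** The number of shared households is not given. As an illustration, assume 12 two-person households among 120 subjects and a within-household correlation of 0.3. The variance then rises by a factor of 1 + (24/120) × 0.3 = 1.06. At R² = 0.03 the net factor is 0.97 × 1.06 = 1.028, and the baseline-only type I error is 2 × [1 − Φ(1.96/√1.028)] = 5.3%. At R² = 0.10 the net factor is 0.954 and the error is 4.5%. The net direction depends on two quantities the document does not give.

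**The case against.** The strongest defence is that nothing important is at risk. The factor most tied to the outcome is already adjusted for, the treatment estimate stays unbiased, this omission does not inflate type I error, and planned power is met with or without the change. All of that stands, and it is why the point is minor.

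Three stronger readings are tempting, and the documents do not support them.

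- A reader might infer that the standard errors are certainly too large. That requires age or gender to be prognostic after baseline. Choosing them as strata suggests the sponsor thinks them relevant, but no figure is given, and at R² = 0 there is no inflation.
- A reader might infer that the benefit of stratifying is thrown away. It is not. Balance still lowers the true variance, and baseline-only power rises with R² (step 4). Comparing adjusted power with a fixed 84.3% would put the gain at about 1.1 to 3.5 points, when like for like it is about 0.6 to 2.2.
- A reader might infer that the trial's p-values are conservative overall. The household rule is not modelled either and can act in the opposite direction (step 8).

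It can also be said that the SAP takes precedence over the protocol (Procedure for Reporting Deviations from the Original Statistical Plan) and might state a fuller model. The supplied file contains no separate SAP text, so the model as written is the one to review.

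**Conclusion.** The mismatch between allocation and analysis is real and is limited to age group and gender. Its consequence is conditional. Over an assumed partial R² of 0 to 0.10, the reported standard error is 0% to 5.4% too large, the type I error is about 5.0% to 3.9%, and between 0 and about 2.2 points of power per comparison are forgone. The plan's claim of at least 80% power holds throughout that range. The figures rest on SD 10 being the residual SD after baseline, on near-ideal balance within strata, and on independent subjects. They describe this omission alone. Severity: minor, an improvement that is close to free.

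**What to change.** In Primary Efficacy Analysis, specify the model as ANCOVA with treatment, the continuous baseline value of the endpoint, age group (≤50, >50) and gender, and use the same model for the secondary endpoints. The continuous baseline takes the place of the three-level bleeding category. If the sponsor prefers baseline only, it should say why.

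The change should be made before unblinding. The plan leaves room for further analyses, and covariates added later would look chosen from the data.

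The cost is one line of wording and 2 of about 107 residual degrees of freedom. Age and gender are already recorded for allocation. If they turn out not to be prognostic, power is unchanged at 84.3%. The household rule needs its own treatment in the analysis, and this change does not address it.
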